#### 9.5.2.2 Description of Procedures/Assessments Schedule

Please refer to the Schedule of Procedures/Assessments ([Table 3](#)).

#### 9.5.3 Appropriateness of Measurements

All clinical assessments are standard measurements commonly used in HCC studies.

Tumor assessments by the investigator will be done using mRECIST criteria (as opposed to RECIST 1.1) as it more appropriately reflects changes in intrahepatic lesions by measuring only the viable portions of the lesions. Other differences between mRECIST and RECIST 1.1 include requiring interval growth for new atypical hepatic lesions before considering them as unequivocal and requiring cytologic evidence of malignancy to consider ascites/effusions as malignant given that underlying cirrhosis is common in HCC subjects ([Lencioni and Llovet, 2010](#)).

The safety assessments to be performed in this study, including hematology analyses, blood chemistry tests, urinalysis, ECGs/echocardiograms, and assessment of AEs, are standard evaluations to ensure subject safety.

#### 9.5.4 Reporting of Serious Adverse Events, Pregnancy, and Events Associated with Special Situations

##### 9.5.4.1 Reporting of Serious Adverse Events

**All SERIOUS ADVERSE EVENTS, regardless of their relationship to study treatment, must be reported on a completed SAE form by email or fax as soon as possible but no later than 1 business day from the date the investigator becomes aware of the event.**

Serious adverse events, regardless of causality assessment, should be collected for 8 weeks after the start of the TPC, or for at least 28 days after the last dose of lenvatinib/TPC if subjects do not continue into the TPC period or do not stay in the TPC period for the 8 weeks of safety monitoring. All SAEs must be followed to resolution or, if resolution is unlikely, to stabilization. Any SAE judged by the investigator to be related to lenvatinib treatment or any protocol-required procedure should be reported to the sponsor regardless of the length of time that has passed since study completion.

**Deaths and life-threatening events should be reported immediately by telephone. The immediate report should be followed up within 24 hours by emailing or faxing the completed SAE form.**

The detailed contact information for reporting of SAEs is provided in the Investigator Study File.

**For urgent safety issues, please ensure all appropriate medical care is administered to the**

subject and contact the appropriate study team member listed in the Investigator Study File.

It is very important that the SAE report form be filled out as completely as possible at the time of the initial report. This includes the investigator's assessment of causality.

Any follow-up information received on SAEs should be forwarded within 1 business day of its receipt. If the follow-up information changes the investigator's assessment of causality, this should also be noted on the follow-up SAE form.

Preliminary SAE reports should be followed as soon as possible by detailed descriptions including copies of hospital case reports, autopsy reports, and other documents requested by the sponsor.

The investigator must notify his/her IRB/IEC of the occurrence of the SAE in writing, if required by their institution. A copy of this communication must be forwarded to the sponsor to be filed in the sponsor's Trial Master File.

#### 9.5.4.2 Reporting of Pregnancy and Exposure to Study Drug Through Breastfeeding

Any pregnancy in a female subject (or partner of a male subject) in which the estimated date of conception is either before the last visit or within 30 days of last dose of study treatment, or any exposure to study drug through breastfeeding during study treatment or within 30 days of last dose of study treatment, must be reported.

If an adverse outcome of a pregnancy is suspected to be related to study drug exposure, this should be reported regardless of the length of time that has passed since the exposure to study treatment.

A congenital anomaly, death during perinatal period, an induced abortion, or a spontaneous abortion are considered to be an SAE and should be reported in the same time frame and in the same format as all other SAEs (see [Section 9.5.4.1](#)).

Pregnancies or exposure to study drug through breastfeeding must be reported by fax or email as soon as possible but no later than 1 business day from the date the investigator becomes aware of the pregnancy. The contact information for the reporting of pregnancies and exposure to study drug through breastfeeding is provided in the Investigator Study File. The Pregnancy Report Form must be used for reporting. All pregnancies must be followed to outcome. The outcome of the pregnancy must be reported as soon as possible but no later than 1 business day from the date the investigator becomes aware of the outcome.

A subject who becomes pregnant must be withdrawn from the study.

#### 9.5.4.3 Reporting of Events Associated with Special Situations

##### 9.5.4.3.1 REPORTING OF ADVERSE EVENTS ASSOCIATED WITH STUDY DRUG OVERDOSE, MISUSE, ABUSE, OR MEDICATION ERROR

Adverse events associated with study drug overdose, misuse, abuse, and medication error refer to AEs associated with uses of the study drug outside of that specified by the protocol. Overdose, misuse, abuse, and medication error are defined as follows:

Overdose	Accidental or intentional use of the study drug in an amount higher than the protocol-defined dose
Misuse	Intentional and inappropriate use of study drug not in accordance with the protocol
Abuse	Sporadic or persistent intentional excessive use of study drug accompanied by harmful physical or psychological effects
Medication error	Any unintentional event that causes or leads to inappropriate study drug use or subject harm while the study drug is in the control of site personnel or the subject.

All AEs associated with overdose, misuse, abuse, or medication error should be captured on the Adverse Event CRF and also reported using the procedures detailed in Reporting of Serious Adverse Events (Section 9.5.4.1) even if the AEs do not meet serious criteria. Abuse is always to be captured as an AE. If the AE associated with an overdose, misuse, abuse, or medication error does not meet serious criteria, it must still be reported using the SAE form and in an expedited manner but should be noted as nonserious on the SAE form and the Adverse Event CRF.

#### 9.5.4.4 Expedited Reporting

The sponsor must inform investigators and regulatory authorities of reportable events, in compliance with applicable regulatory requirements, on an expedited basis (ie, within specific time frames). For this reason, it is imperative that sites provide complete SAE information in the manner described above.

#### 9.5.4.5 Breaking the Blind

Not applicable

#### 9.5.4.6 Regulatory Reporting of Adverse Events

Adverse events will be reported by the sponsor or a third party acting on behalf of the sponsor to regulatory authorities in compliance with local and regional law and established guidance. The format of these reports will be dictated by the local and regional requirements.

### 9.5.5 Completion/Discontinuation of Subjects

A subject may elect to discontinue the study at any time for any reason. All subjects who discontinue the study are to complete the study's early discontinuation procedures indicated in the Schedule of Procedures/Assessments ([Table 3](#)).

The investigator will promptly explain to the subject involved that the study will be discontinued for that subject and provide appropriate medical treatment and other necessary measures for the subject. A subject who has ceased to return for visits will be followed up by mail, phone, or other means to gather information such as the reason for failure to return, the status of treatment compliance, the presence or absence of AEs, and clinical courses of signs and symptoms.

Subjects who discontinue early from the study will be discontinued for 1 of these primary reasons: AE(s), lost to follow-up, subject choice, progression of disease, withdrawal of consent, pregnancy, study terminated by sponsor, or other. In addition to the primary reason, the subject may indicate 1 or more secondary reason(s) for discontinuation. Study disposition information will be collected on the Subject Disposition CRF.

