#### 9.1.2.3 Follow-Up Period (Survival Follow-Up)

The Follow-Up Period will begin immediately after the final visit of the subsequent TPC period (Treatment Period 2). Subjects will be followed every 12 weeks for survival and will continue as long as the study subject is alive or the subject withdraws consent. If the investigator deems a subject inappropriate for commercially available subsequent systemic TPC, the subject will be followed for survival every 12 weeks after the lenvatinib Off-Treatment Visit of the Lenvatinib Treatment Period (Treatment Period 1). Subjects' survival status and all additional anticancer treatments received will be recorded.

The sponsor may decide to terminate survival follow-up of subjects after the completion of the primary analysis or when all subjects have discontinued study treatment.

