##### 9.5.1.5.1 ADVERSE EVENTS

An AE is any untoward medical occurrence in a patient or clinical investigation subject administered an investigational product. An AE does not necessarily have a causal relationship with the medicinal product.

The criteria for identifying AEs in this study are:

- Any unfavorable and unintended sign (including an abnormal laboratory finding), symptom, or disease temporally associated with the use of an investigational product, whether or not considered related to the investigational product (Note: Every sign or symptom should not be listed as a separate AE if the applicable disease [diagnosis] is being reported as an AE).
- Any new disease or exacerbation of an existing disease. However, worsening of the primary disease (HCC) should be captured under efficacy assessments as disease progression rather than as an AE. If the disease progression leads to an untoward medical occurrence, then this medical occurrence should be recorded as an AE.

- Any deterioration in nonprotocol-required measurements of a laboratory value or other clinical test (eg, ECG or x-ray) that results in symptoms, a change in treatment, or discontinuation of study drug.
- Recurrence of an intermittent medical condition (eg, headache) not present pretreatment (Baseline).
- An abnormal laboratory test result should be considered an AE if the identified laboratory abnormality leads to any type of intervention, withdrawal of study drug, or withholding of study drug, whether prescribed in the protocol or not.

All AEs observed during the study will be reported on the CRF. All AEs, regardless of relationship to study drug or procedure, should be recorded beginning from the time the subject signs the study ICF through the last visit and for 28 days after the last dose of lenvatinib treatment if subjects do not enter TPC period, or for 8 weeks after the start of TPC period. SAE information should be collected for 8 weeks after the start of the TPC, or for at least 28 days after the last dose of lenvatinib/TPC if subjects do not continue into the TPC period or do not stay in the TPC period for the 8 weeks of safety monitoring.

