**Table 3 Schedule of Procedures/Assessments in Study E7080-M001-222**

Period	Screening a	Baseline a	Lenvatinib (Treatment Period 1) (All cycles are 28 days in duration)									TPC (Treatment Period 2)					Survival FU
			3	4	5	6	7	8, 9, etc		99							
Visit	1	2	Cycle 1 b		Cycle 2 c		Cycle 3 – Last c		Lenvatinib Off-Treatment Visit	TPC Baseline	Week 2	Week 4	Week 8	Week 16 aa	Every 12 weeks		
Day	-21 to -2	-1	1	8	15	1	15	1									
Procedures/ Assessments																	
Informed consent	X																
Inclusion/exclusion criteria	X	X															
Demographic data	X																
ECOG-PS d	X	X			X		X			X	X d	X	X	X			
NYHA d	X																
BCLC staging	X																
Medical/surgical history	X	X															
Gastroenterological endoscopy e	X																
Virus tests (HIV Ab, HCV Ab, HBsAg) f	X																
Phone contact or visit g				X													
Vital signs and weight h,i	X	X	X		X	X	X	X		X h	X	X	X				
Physical examination j	X	X k		X	X		X			X j	X	X	X				
12-Lead ECG l	X				X		X			X l	X	X	X				
MUGA scan or echocardiogram m	X									X							

Period	Screening a	Baseline a	Lenvatinib (Treatment Period 1) (All cycles are 28 days in duration)									TPC (Treatment Period 2)					Survival FU
			1	2	3	4	5	6	7	8, 9, etc		99					
Visit	1	2	3	4	5	6	7	8, 9, etc		99							
Day	-21 to -2	-1	Cycle 1 b			Cycle 2 c		Cycle 3 – Last c		Lenvatinib Off-Treatment Visit	TPC Baseline	Week 2	Week 4	Week 8	Week 16 aa	Every 12 weeks	
			1	8	15	1	15	1	15								
Procedures/ Assessments																	
Hematology and chemistry n	X	X			X	X	X	X		X	X n	X	X	X			
Urinalysis o,i	X	X			X	X	X	X	X	X	X i	X	X	X			
Pregnancy test p	X	X															
Child-Pugh score d	X	X			X		X			X	X d	X	X	X			
PRO-CTCAE questionnaires q										X	X q	X	X	X	X		
Blood coagulation test (PT/INR)	X	X			X		X			X							
Special chemistries r	X	X			X	X		X		X	X r			X	X		
Biomarker (whole blood) s		X															
Biomarker (serum/plasma) sample s			X		X	X		X		X	X s			X	X		

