- n: Clinical laboratory tests (hematology and clinical chemistry) will be performed at local laboratory. Laboratory tests at Baseline may be performed up to 72 hours prior to first dose of lenvatinib treatment. Review hematology clinical chemistry results within 48 hours after receiving quick estimation. Assessments scheduled may be performed within 72 hours prior to the visit. If  $\geq$  Grade 3 hematologic or clinical chemistry toxicities, repeat laboratory test and AE assessment at least every 7 days (until improvement to  $<$ Grade 3). Clinical laboratory tests will be performed at week 2, week 4, and week 8 ( $\pm 1$  week) in TPC period. A TPC baseline assessment should be performed unless the lenvatinib Off-Treatment visit is completed  $\leq 7$  days prior to the first TPC treatment.
- o: For subjects with proteinuria  $\geq 2+$  (see the dose adjustment table for management of proteinuria).
- p: A serum or urine pregnancy test will be performed in women of childbearing potential (ie, premenopausal women and postmenopausal women who have been amenorrheic for less than 12 months). A separate baseline assessment is required if a negative screening pregnancy test was obtained more than 72 hours before the first dose of study drug.
- q: PRO-CTCAE data will be collected at the following time points: lenvatinib Off-Treatment Visit during Treatment Period 1, every 2 weeks for the first 4 weeks, and then at week 8 and week 16 ( $\pm 1$  week) in Treatment Period 2. A TPC baseline assessment should be performed unless the lenvatinib Off-Treatment visit is completed  $\leq 7$  days prior to the first TPC treatment.
- r:  $\alpha$ -Fetoprotein (AFP) and thyroid-stimulation hormone (TSH) will be measured at screening visit, Baseline, on C1D15, C2D1, C3D1, and every 2 cycles thereafter (C5D1, C7D1, C9D1, etc) in Treatment Period 1, and week 8 and week 16 ( $\pm 1$  week) in TPC period. A TPC baseline assessment should be performed unless the lenvatinib Off-Treatment visit is completed  $\leq 7$  days prior to the first TPC treatment.

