Subjects entering subsequent treatment period (TPC period) should have TPC period baseline tumor assessments performed unless the last tumor assessment performed in lenvatinib treatment period is less than 28 days before the subsequent treatment starts, in which case those scans may be used as the TPC period baseline. A new tumor assessment baseline (selection of target and non-target lesions and calculation of a new baseline sum of diameters (SOD) must be established before beginning TPC. **Subjects will continue tumor assessments during subsequent TPC every 8 weeks ( $\pm 1$  week) or until disease progression, subject death, withdrawal or loss to follow-up.** Detailed image acquisition guidelines will be provided by the imaging core laboratory.

- u: Screening CT of the brain with contrast or MRI of the brain pre- and post-gadolinium should be performed within 28 days prior to the first dose of study treatment. During the study drug treatment period, CT/MRI of the brain should be performed if clinically indicated. The same methodology and scan acquisition techniques used at screening should be used throughout the study to ensure comparability.
- v: An archival tumor sample from the most recent surgery or biopsy for identification of predictive biomarkers and pathology review may be collected at screening or at any time during the study, unless no such material is available.
- w: Subjects who do not take subsequent TPC will be followed for survival every 12 weeks after the Off-Treatment visit. Otherwise, subjects will be followed for survival every 12 weeks after the final Visit in the subsequent TPC period. If a clinic visit is not feasible, follow up information may be obtained via telephone or email. Subjects' survival status and all additional anticancer treatments received will be recorded.
- x: Treatment dose and schedule on Prescribing Information of commercially available TPC should be followed.
- y: Concomitant meds will be recorded for 28 days after last dose of lenvatinib treatment if subjects do not enter TPC period, or for 8 weeks after the start of TPC period or up to 28 days after last dose of TPC if subject does not stay in the TPC period for the 8 weeks of safety monitoring. All anticancer therapy will be recorded until time of death or termination of survival follow-up. Prior medication information before screening should be collected at the screening period.

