#### 9.7.1.8.5 ELECTROCARDIOGRAMS

Descriptive statistics for ECG parameters and changes from baseline will be presented by visit. Change from baseline to each postbaseline visit and to end of treatment in ECG findings will be summarized by visit.

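### Table 3 defines no end-of-TPC assessment although other sections rely on one, so supporting safety and PRO-CTCAE data can be missing selectively in subjects who stop TPC early

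*Combined protocol and SAP*

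**What the plan says.** Treatment Period 1 closes with a lenvatinib Off-Treatment Visit, which has its own column in Table 3. Treatment Period 2 has TPC Baseline, Week 2, Week 4, Week 8 and Week 16, and the next column is survival follow-up every 12 weeks. No column or footnote covers the end of TPC or an early stop.

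Other parts of the protocol assume that such an assessment exists:

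- Section 9.5.5: "All subjects who discontinue the study are to complete the study's early discontinuation procedures indicated in the Schedule of Procedures/Assessments".
- Section 9.1.2.3: "The Follow-Up Period will begin immediately after the final visit of the subsequent TPC period". The synopsis and Section 9.3.3 say the same.
- Table 3, footnote w: "Otherwise, subjects will be followed for survival every 12 weeks after the final Visit in the subsequent TPC period".
- Section 9.7.1.8.5: "Change from baseline to each postbaseline visit and to end of treatment in ECG findings will be summarized by visit". Section 9.7.1.8.3 adds laboratory shift tables to the worst and to the final post-baseline grade. Section 9.7.1.8 requires all safety analyses for each treatment period.

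The TPC assessments are tied to fixed weeks. For laboratory tests, footnote n says "Clinical laboratory tests will be performed at week 2, week 4, and week 8". ECG, vital signs, physical examination, urinalysis, ECOG and Child-Pugh follow the same weeks. PRO-CTCAE adds Week 16. Under footnote aa, only tumor assessment and TPC dose are collected after Week 16.

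**The concern.** The primary objective is the safety and tolerability of TPC, yet TPC is the one treatment period without an exit assessment. A subject who stops in week 5 or 6 has the last scheduled laboratory tests, ECG, Child-Pugh score and PRO-CTCAE at Week 4. Section 9.5.1.5.1 describes subjects who "do not stay in the TPC period for the 8 weeks of safety monitoring", and follow-up begins immediately after the undefined final visit. Read together, these suggest that such a subject does not return for Week 8.

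If so, the missing values are related to the outcome. Subjects absent at Week 8 (and, for PRO-CTCAE, at Week 16) are those who stopped, and some stopped because they did not tolerate treatment. By-visit laboratory, ECG, Child-Pugh and PRO-CTCAE summaries then come mainly from those who did tolerate it. The final-grade and end-of-treatment summaries for Period 2 would use a value from before the stop, of uncertain age. PRO-CTCAE burden in the TPC period is a stated exploratory objective.

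**Working it through.** **The plan's own figure.** The only precision statement is Table 4. The Wald half width 1.96 × √(0.75 × 0.25 / n) for n = 100, 90, 80, 70, 60 and 50 gives 8.49, 8.95, 9.49, 10.14, 10.96 and 12.00%, in agreement with the printed values. It concerns the Grade ≥3 TEAE rate and does not depend on an end-of-TPC visit, so this point leaves it untouched.

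**What relies on an end-of-TPC assessment, and what Table 3 supplies.**

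| Place | What it needs | What Table 3 supplies for TPC |
|---|---|---|
| 9.5.5 | early-discontinuation procedures | none |
| Synopsis, 9.1.2.3, 9.3.3, footnote w | a final TPC visit | no such column or definition |
| 9.7.1.8.5 with 9.7.1.8 | end-of-treatment ECG for each period | ECG at baseline and Weeks 2, 4, 8 |
| 9.7.1.8.3 with 9.7.1.8 | final laboratory grade for each period | laboratory tests at baseline and Weeks 2, 4, 8 |

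**Schedule gaps.** Laboratory tests, ECG and Child-Pugh fall at weeks 0, 2, 4 and 8, with gaps of 2, 2 and 4 weeks and nothing scheduled afterwards. PRO-CTCAE falls at weeks 0, 2, 4, 8 and 16, with gaps of 2, 2, 4 and 8 weeks. For a stop before Week 8, the last scheduled laboratory test can be about 4 weeks old (plus the 1-week visit window). For a stop after Week 8 it can be older, without limit.

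**How many subjects.** The documents give no time on TPC. I assume exponential time on TPC with a median of 2 to 6 months (1 month = 4.348 weeks), and 50 recipients. The 50 is the lower end of Table 4, since Section 9.7.2 assumes that more than 50% of 100 subjects receive TPC. With weekly rate λ = ln 2 / median and S(t) = exp(−λt):

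| | Median 2 months | Median 6 months |
|---|---|---|
| Median in weeks; λ | 8.70; 0.0797 | 26.09; 0.0266 |
| Stop before Week 8: 1 − S(8) | 0.47 | 0.19 |
| of 50 | 24 | 10 |
| Stop in weeks 0–1: 1 − S(1) | 0.077 | 0.026 |
| Stop in weeks 5–7: S(5) − S(7) | 0.671 − 0.572 = 0.099 | 0.876 − 0.830 = 0.045 |
| More than 1 week from an on-treatment visit | 0.176 | 0.072 |
| of 50 | 9 | 4 |

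The last two rows count stops before Week 8 that lie more than 1 week from Weeks 2, 4 and 8. Stops in weeks 1–3, 3–5 and 7–8 lie within 1 week of one of those visits. TPC Baseline is not counted because it precedes exposure. All counts are for any cause, so stops for toxicity are a subset.

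**The case against.** The strongest reply is that the primary endpoint is not at risk. It is analysed as the incidence of TEAEs and SAEs. AEs are recorded for 8 weeks after the start of TPC, and SAEs for at least 28 days after the last TPC dose when a subject leaves before 8 weeks. Concomitant medications are also recorded for up to 28 days after that dose, and SAEs are followed to resolution or stabilization. This stands. A reader might infer that the schedule gap biases the primary tolerability result favourably, or that the next planned contact after an early stop is only a survival check. The documents support neither. Some abnormalities count as AEs only once a test finds them, so under-detection is conceivable, but nothing in the documents lets one show it or size it.

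A reader might also infer that early stoppers leave with no laboratory tests at all. That is too absolute. Footnote n and Section 9.5.1.5.3 require repeat tests at least every 7 days for Grade ≥3 haematologic or chemistry toxicity until it falls below Grade 3. This protects severe abnormalities already found. It does not detect new ones, and it does not cover ECG, Child-Pugh or PRO-CTCAE.

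The sentence in Section 9.5.5 concerns leaving the study. Section 9.3.3 allows a subject to stop treatment but continue off-treatment visits, and the Week 2, 4 and 8 visits are not made conditional on dosing. So the text is ambiguous on whether an early stopper attends Week 8; it does not rule it out. But the ambiguity is itself a defect, because sites may resolve it differently. The final-visit wording and the planned summaries carry the point without Section 9.5.5.

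Finally, end of treatment in the ECG section may simply mean the last on-treatment value, and Section 9.7 leaves detail to a separate SAP. That could settle the definition, but an analysis plan cannot supply a measurement that was never scheduled.

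**Conclusion.** The point holds as a gap in the schedule with a consequence for supporting data. Table 3 has no end-of-TPC assessment, while Sections 9.1.2.3, 9.3.3, 9.5.5, 9.7.1.8.3 and 9.7.1.8.5 and footnote w rely on one. Followed as written, the schedule can lose laboratory, ECG, Child-Pugh and PRO-CTCAE data selectively in subjects who stop TPC between visits. No bias in TEAE or SAE incidence is shown, and the precision in Table 4 is unaffected.

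On size, the 19% to 47% stopping before Week 8 (10 to 24 of 50) should not be read as subjects with no assessment at stopping. It counts every cause, including progression and death, and includes stops close to a visit. About 4 to 9 of 50 is the fairer figure for stops before Week 8. It rests on the assumed exponential distribution, on medians of 2 to 6 months that come from no document, and on 50 recipients. It also assumes that early stoppers do not return for later visits, which the text suggests but does not state. This should be corrected, but it does not threaten the primary analysis.

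**What to change.** Add an End of TPC column to Table 3.

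- **Stop before Week 8:** perform the existing Week 8 safety and PRO-CTCAE panel as close as practicable to the stop, no later than the Week 8 window, in place of the Week 8 visit.
- **Stop between Weeks 8 and 16:** bring forward only what Week 16 already schedules, including PRO-CTCAE. Do not extend the laboratory, ECG and Child-Pugh panel beyond Week 8.
- **Definitions:** name this assessment as the final visit of the TPC period, point Section 9.5.5 to it, and state from which date survival contact is counted when TPC stops after Week 16.
- **Analysis:** in Section 9.7.1.8 and the SAP, use it as the Period 2 end-of-treatment or final value in the ECG summary, the laboratory shift tables and the PRO-CTCAE summaries. For stops after Week 8, use the last available laboratory and ECG value and say so.

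The cost is an amendment to Table 3 and at most one clinic visit per early stopper. Before Week 8 that visit replaces one already scheduled. No new type of assessment is needed.
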